7.6.5.2 Confirmed Adjudicated Cardiovascular Adverse Events

The number and percentage of subjects with confirmed cardiovascular events (i.e., hospitalization for heart failure as determined by the adjudication committee) will be summarized by preferred term and treatment group.

In this study, only events of heart failure requiring hospitalization will be adjudicated.

7.6.5.3 Confirmed Adjudicated Hepatic Adverse Events

The number and percentage of subjects with confirmed hepatic events (as determined by the adjudication committee) will be summarized by preferred term and treatment group.

In this study, the following hepatic events will be adjudicated:

- AST and/or ALT >3 X ULN and TB >2 X ULN (within 14 days of the AST and/or ALT elevation)

- AST and/or ALT >10X ULN
- Hepatic event AE/SAE occurring within 30 days before subject death

In addition, a listing of all adjudicated hepatic adverse events by subjects will be provided.

7.6.5.4 Confirmed Adjudicated DKA Events

The number and percentage of subjects with confirmed DKA events (as determined by the adjudication committee) will be summarized by preferred term (as listed in Appendix B of the DKA Adjudication Charter v3.0 dated 17 July 2018) and treatment group.

7.6.5.5 Other AEOSIs

Other adverse events of special interest (AEOSI) will be defined based on lists of preferred terms. These lists will be reviewed and finalized prior to database lock and unblinding of the database.

The following summaries and listing of AEOSI will include all data regardless of use of rescue medication:

- AEs of genital infection by recurrence
- AEs of genital infection by gender
- AEs of Urinary Tract Infection (UTI) by recurrence
- AEs of UTI by gender
- AEs of severe cutaneous adverse reactions (SCAR)
- AEs of renal impairment/failure
- AEs of volume depletion
- AEs of fracture
- AEs of liver injury
- AEs of hypersensitivity reactions
- AEs of decreased lymphocyte count
- AEs of pancreatitis
- AEs of Breast, bladder, prostate and pancreatic cancer
- AEs of cardiac failure
- AEs of decreased thrombocyte count

The number and percentage of subjects with each of these events will be summarized by preferred term and treatment group in the short-term treatment period and in the combined short- and long-term treatment periods.

The number and percentage of subjects with events of urinary-tract infection will be summarized for the subgroups defined on the basis of categorized variables including incidence (1, 2, 3, or > 3). A similar summary will be produced for events of genital infection.

7.6.6 Laboratory Evaluation

Unless otherwise specified, laboratory data (Glucagon, proinsulin, hematology and chemistry assessments, UACR, C-Reactive Protein (biomarker), N Terminal ProB Type Natriuretic Peptide

(biomarker) obtained after the start of study medication dosing up to and including 4 days (30 days for liver function laboratory tests) after the last short-term double-blind dosing date (or up to and including the start of the long-term treatment period, whichever comes first) will be considered as obtained during the short-term double-blind treatment period. Laboratory data obtained from the day after the last study medication + 4 days (30 days for liver function laboratory tests) up to the last visit date of the follow-up period will be considered as obtained during the follow-up period. Laboratory data obtained after the start of short-term treatment up to and including 4 days (30 days for liver function laboratory tests) after the last dose of short- or long-term medication will be considered as obtained during the combined short- and long-term treatment periods.

Listings for lab data will include everything in the database.

For liver safety, a summary of proportion of subjects with elevated liver test including elevated AT (ALT and/or AST) and total bilirubin (see Appendix 3 for definition) will be provided. In addition, a summary of proportion of subjects with elevated liver test and/or reported AE of hepatic disorder will also be provided.

Because the mechanism of action of dapagliflozin is known to impact urine glucose levels, urinalysis results of glucose will not be summarized. All laboratory evaluations performed by central laboratories will be included in summary tables. All laboratory tables for the CSRs will be produced in both conventional and SI units whenever available.

7.6.6.1 Marked Laboratory Abnormalities

Laboratory abnormalities will be evaluated based on marked abnormality values (MA). The pre-defined criteria for marked abnormalities are detailed in Appendix 3. If both the baseline and on-treatment values of a parameter are beyond the same MA limit for the parameter, then the on-treatment value will be considered a MA only if it is more extreme (farther from the limit) than was the baseline value. If the baseline value is beyond the low MA limit, and the post-baseline value is beyond the high MA limit (or vice-versa), then the post-baseline value will be considered a MA.

Laboratory abnormalities occurring during the short-term double-blind treatment period and the combined short- and long-term treatment periods will be summarized by treatment group. In the short-term double-blind treatment period, the summaries will be presented for both the primary and sensitivity safety analyses. The direction of change (high or low) in MA will be indicated in the tables.

For each subject with an MA for a parameter, all the subject's values of that parameter will be listed.

7.6.6.2 Change from Baseline for Selected Laboratory Parameters Over Time

All analyses of laboratory data will use observed data regardless of rescue. Visit windows are provided in Section 8.3 in order to link each laboratory test to a scheduled visit. Change from baseline during the short-term treatment period and the combined short- and long-term treatment periods for selected laboratory parameters will be summarized descriptively by treatment group using n's, means, medians, SEs, and 95% CIs.

- hematocrit
- hemoglobin
- platelet count
- white blood cell (WBC) count
- total bilirubin
- alanine aminotransferase (ALT)
- alkaline phosphatase
- aspartate aminotransferase (AST)
- Estimated GFR using MDRD equation:
$$\text{eGFR (mL/min/1.73m}^2\text{)} = 175 \times (\text{Scr})^{-1.154} \times (\text{Age})^{-0.203} \times (0.742 \text{ if female}) \times (1.210 \text{ if African-American})$$
- creatinine kinase (creatine phosphokinase) (CK)
- creatinine, serum (S_{Cr})
- electrolytes - sodium, potassium, chloride, magnesium and calcium
- total protein, serum
- inorganic phosphorus
- urinary albumin to creatinine ratio
- creatinine clearance

Change from baseline in categorical variables will be provided using shift tables. For urinary albumin to creatinine ratio, the shift table will be derived from laboratory assessments after the date of first dose of short-term double-blind study medication up to and including 4 days following the date of last dose of short-term and long-term study medication, or up to the end date of the short-term and long-term treatment period, whichever comes first. Week 156 value in the shift table is chosen for Week 156 using the day range of 1003 to last day of long-term treatment as in SAP table 8.4H, regardless of rescue medication, and up to and including 4 days following the date of last dose of short-term + long term study medication. If no week 156 value available then last available post-baseline observation prior to week 156 should be used (imputed) for Week 156 in the shift table (i.e., LOCF)

7.6.7 Vital Signs

Vital signs data obtained after the start of study medication dosing up to and including 4 days after the last short-term double-blind dosing date (or up to and including the start of the long-term treatment period, whichever comes first) will be considered as obtained during the short-term double-blind treatment period.

Vital signs data obtained after the start of study medication dosing up to and including 4 days after the last short- or long-term dosing date will be considered as obtained during the combined short- and long-term treatment period.

Visit windows are provided in Section 8.3 in order to link each vital sign measurement to a scheduled visit. Values and changes from baseline for vital sign measurements will be summarized

by treatment group at each scheduled visit using descriptive statistics (using available data regardless of rescue for subjects in Treated Subjects Data Set) for BMI, waist circumference, sitting SBP, DBP and HR, only.

7.6.8 Electrocardiograms

The normality/abnormality of the ECG tracing, as determined by the investigator, will be summarized using frequency tables on number of subjects who have a normal/abnormal ECG tracing at Week 52 and at Week 156 by the ECG tracing at baseline.

7.6.9 Pregnancy Test Results

By-subject listings of pregnancy test results will be provided using Treated Subject Data Set for the short-term and the combined short- and long-term treatment periods.

8 CONVENTIONS

Data collected outside the analysis window (defined in Section 8.4) after subjects discontinued double-blinded study medication will be excluded from analyses.

8.1 Duration of Type 2 Diabetes

Duration of Type 2 diabetes is calculated as the number of years from Type 2 diabetes diagnosis date to informed consent date:

$(1 + \text{consent date} - \text{diagnosis date}) / 365.25$.

The duration of diabetes will be included in the baseline diabetes characteristics listing.

If the date Type 2 diabetes was diagnosed is partially missing, the following rules will take effect:

- Missing day, but month and year are present: the day will be imputed as the 15th day of the month.
- Missing day and month, but year is present: the day and month will be imputed as 30 June of the year (provided that the imputed date is less than the consent date).
- Missing year, but day and month are present: No imputations will occur, and the subject will be excluded from all summaries related to duration of Type 2 diabetes.
- Missing day, month and year: No imputations will occur, and the subject will be excluded from all summaries related to duration of Type 2 diabetes.
- If any such imputed date falls after the consent date, then the diagnosis date will be taken as equal to the consent date.

These durations, even if partially imputed, will be listed. However, only the portion of the date of diagnosis actually observed, rather than imputed dates, will be displayed in listings.

8.2 Missing and Multiple Measurements

For listings of efficacy and safety measures, missing values will be represented as not reported.

If the blood pressure measurements are taken at a wrong position, e.g., sitting instead of standing, then these measurements will be excluded from the summary/analysis.

Some laboratory samples may be inadvertently analyzed multiple times for the same test, producing multiple lab results on the same collection date and time for the same subject.

In case of multiple observations within a single visit window, the following rules apply:

- If there are two or more observations within the same visit window, the non-missing observation closest to the target day will be used in the analysis
- If two observations are equidistant from the target day, the non-missing observation with the later collection date will be used in the analysis
- If two or more observations are collected on the same day and have a collection time associated with them, the non-missing observation with the later collection time will be used in the analysis
- If two or more observations are collected on the same day and time, all non-missing and the average of the observations will be used in the analysis.
- If two or more observations are collected on the same day, all non-missing but with no collection time associated with at least one of them, the average of the observations will be used in the analysis.
- For MRI visits, values from an earlier visit will be used instead of values at Week 52/122 for patients who were rescued or prematurely discontinued prior to Week 52/122. MRIs from week 52/122 could have been scheduled up to 4 weeks after the Rescue or Premature Treatment Discontinuation Date.

If a visit window does not contain any observations, the data will be missing for that visit.

8.3 Laboratory Evaluations

All laboratory evaluations performed by central laboratories and local laboratories that are included in the database will be listed but only the data from central lab will be included in summary tables.

8.3.1 Post-treatment Efficacy and Safety Evaluations

While efficacy and safety observations will be listed regardless of whether the subject was taking double-blind study drug, observations may not contribute to summaries/analyses if they are measured after the last dose of the double-blind study medication given during the treatment periods, as indicated below:

For efficacy parameters:

- Lipids, glucagon, proinsulin, uACR, biomarkers (C-reactive protein, N-terminal ProB-type Natriuretic Peptide) and SBP will be summarized only if measured on or prior to the 4th day after the last study drug treatment date.
- FPG, fasting C-peptide, fasting insulin, HOMA assessments and spot urinary glucose to creatinine ratio will be summarized/analyzed only if measured on or prior to the first day after the last study drug treatment date.
- HbA1c, BMI, waist circumference and body weight will be summarized/analyzed only if measured on or prior to the 8th day after the last study drug treatment date.

For safety parameters:

- SAEs, including hypoglycemia, reported as SAEs, and the lab measurements for the liver function tests will be included in the summaries only if occurred/measured on or prior to the 30th day after the last study drug treatment date.
- All other safety events (non-serious AEs, non-serious hypoglycemia, etc.) and measurements (safety lab, vital signs, etc.) will be included in the summaries only if occurred/measured on or prior to the 4th day after the last study drug treatment date.

8.4 Longitudinal Assessments

Day 1 for the short-term double-blind treatment period is the start date of short-term double-blind treatment medication.

Visit windows are specified below.

Table 8.4 A: Vital Signs and FPG Visit Windows for the Short-term Analyses

Visit	Treatment Period	Target Day	Day Range
Week 3	ST	22	2-35
Week 6	ST	43	36-64
Week 12	ST	85	65-99
Week 16	ST	113	100-155
Week 28	ST	197	156-239
Week 40	ST	281	240-323
Week 52	ST	365	324 to last day of ST double-blind treatment

Table 8.4 B: Vital Signs (except BMI and Waist Circumference), FPG Visit Windows for the Short and Long-term Analyses

Visit	Treatment Period	Target Day	Day Range
Week 3	ST	22	2-35
Week 6	ST	43	36-64
Week 12	ST	85	65-99
Week 16	ST	113	100-155
Week 28	ST	197	156-239
Week 40	ST	281	240-323
Week 52	ST	365	324 to last day of ST double-blind treatment
Week 65	LT	456	First day of long-term treatment -501
Week 78	LT	547	502-592
Week 91	LT	638	593-683
Week 104	LT	729	684-774
Week 117	LT	820	775-865

Table 8.4 B: Vital Signs (except BMI and Waist Circumference), FPG Visit Windows for the Short and Long-term Analyses

Visit	Treatment Period	Target Day	Day Range
Week 130	LT	911	866-956
Week 143	LT	1002	957-1047
Week 156	LT	1093	1048 to last day of long-term treatment

Table 8.4 C: BMI - Visit Windows for the Short and Long-term Analyses

Visit	Treatment Period	Target Day	Day Range
Week 28	ST	197	2-281
Week 52	ST	365	282 to last day of ST double-blind treatment
Week 65	LT	456	First day of long-term treatment -501
Week 78	LT	547	502-592
Week 91	LT	638	593-683
Week 104	LT	729	684-774
Week 117	LT	820	775-865
Week 130	LT	911	866-956
Week 143	LT	1002	957-1047
Week 156	LT	1093	1048 to last day of long-term treatment

Table 8.4 D: Waist Circumference - Visit Windows for the Short and Long-term Analyses

Visit	Treatment Period	Target Day	Day Range
Week 28	ST	197	2-281
Week 52	ST	365	282 to last day of ST double-blind treatment
Week 65	LT	456	First day of long-term treatment -638
Week 117	LT	820	639-956
Week 156	LT	1093	957 to last day of long-term treatment

Table 8.4 E: HbA1c- Visit Windows for the Short-term Analyses

Visit	Treatment Period	Target Day	Day Range
Week 12	ST	85	2-99
Week 16	ST	113	100-155
Week 28	ST	197	156-239

Visit	Treatment Period	Target Day	Day Range
Week 40	ST	281	240-323
Week 52	ST	365	324 to last day of ST double-blind treatment

Table 8.4 F: HbA1c-- Visit Windows for the Short- and Long-term Analyses

Visit	Treatment Period	Target Day	Day Range
Week 12	ST	85	2-99

Week 52	ST	365	Day 2 to last day of ST double-blind treatment
Week 104	LT	729	First day of long-term treatment - 911
Week 156	LT	1093	912 - last day of long-term treatment

Table 8.4 M: MRI - Visit Windows for the Short-term Analyses

Visit	Treatment Period	Target Day	Day Range
Week 52	ST	365	Day 2 to (last day of ST double-blind treatment + 27 days)

Table 8.4 N: MRI – Visit Windows for the Short and Long-term Analyses

Visit	Treatment Period	Target Day	Day Range
Week 52	ST	365	Day 2 to (last day of ST double-blind treatment + 27 days)
Week 122	LT	855	First day of long-term treatment to last day of long-term treatment (exclude assessments that were within 27 days from last day of ST double-blind treatment and were assigned to Week 52 analysis visit)

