All MRI consented subjects should have MRI visits scheduled at the imaging site in close proximity to the Day 1 (Randomization), Week 52 and Week 122 visits at the clinical sites. The MRI assessments do not need to occur on the same day as these visits. An ad-hoc visit at the imaging site will be scheduled within 2 weeks prior to the Day 1 (Randomization) visit (eg, between Week -2 and up to, but not including, Day 1). Ad-hoc visits at the imaging site will be scheduled within ± 2 weeks of the Week 52 visit (eg, between Week 50 up to Week 54) and within ± 4 weeks of the Week 122 visit (eg, between Week 118 up to Week 126). Additionally, subjects who require rescue therapy or discontinue from study treatment early will be asked to return for an unscheduled MRI visit (if possible) within 4 weeks of initiating rescue medication or the Early Termination visit.

All MRIs will be sent for central evaluation to a core laboratory. No local reading will be performed. During the double-blinded short-term treatment period (Day 1 to Week 52), the MRI results will be blinded to recruiting sites, investigators, the MRI sites, the subjects, and the Sponsor. After Week 52, the MRI results will not be blinded for the Sponsor, but will remain blinded to the recruiting sites, investigators, the MRI sites, and the subjects. Subjects who are found to have unevaluable data at baseline will be removed from the MRI sub-study population but will remain active in the base study through trial completion. Additional subjects will be added to obtain the protocol required subpopulation.

Any incidental findings of potential clinical relevance that are not directly associated with the objectives of the protocol should be evaluated and handled by the investigator as per standard medical/clinical judgment.

The Sponsor will not provide MRI results to subjects or investigators at the conclusion of the study, unless specifically requested by the subject.

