7.5.5.4 Mean Change from baseline in endpoints for sub-study

In the CGM sub-study, CGM will be performed for periods of 7 days at baseline and at Week 52 of treatment. Mean amplitude of glucose excursions (MAGE) for a 24-hr period is calculated in the way defined in Section 7.1.3. The average of the 7 MAGE values at baseline or at Week 52 will be used for analyses. Analyses of the mean change from baseline in MAGE at Week 52 will be performed using the ANCOVA model based on LOCF data.

In the MRI-PDFP sub-study, the mean change from baseline in visceral and subcutaneous adipose tissue volume and percent hepatic lipid content as assessed by MRI at Week 52 will be performed using the ANCOVA model based on LOCF data.

The analysis of the mean change from baseline in visceral and subcutaneous adipose tissue volume and percent hepatic lipid content as assessed by MRI at the Week 122 CRF visit will be performed using the same longitudinal repeated measures model as described in Section 7.1.2.

MRI values from an earlier visit are used instead of values at Week 52/122 for patients who are rescued or prematurely discontinued prior to Week 52/122. MRIs from week 52/122 could have been scheduled up to 4 weeks after the Rescue or Premature Treatment Discontinuation Date.

The analysis of percent hepatic lipid content will be adjusted for baseline weight.

Liver fat fraction (%) will also be summarized in a shift tables from baseline to week 52 (in the ST summary), and weeks 52 and 122 (in the ST+LT summary), using categories of $\geq 5.5\%$ and $< 5.5\%$.

For MRI laboratory data (visceral adipose tissue, subcutaneous adipose tissue and liver fat function) obtained from day 2, up to and including the last short-term double-blind dosing date + 27 days (see Table 8.4M) will be considered as obtained during the short-term double-blind treatment period. MRI laboratory data obtained from the day after the last study medication up to the last visit date of the follow-up period will be considered as obtained during the follow-up

period. MRI laboratory data obtained from the first day of long-term treatment up to including the last day of long-term medication (excluding assessments that were within 27 days from last day of ST double-blind treatment and were assigned to Week 52 analysis visit) will be considered as obtained during the combined short- and long-term treatment periods.

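### The SAP contradicts itself on whether an early-termination MRI taken after the last long-term dose counts at Week 122

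*SAP*

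**What the plan says.** **Rules that close the Week 122 window at the last dose**

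- SAP 8.4, Table 8.4 N, Week 122 row: "First day of long-term treatment to last day of long-term treatment (exclude assessments that were within 27 days" of the last short-term dose and already assigned to Week 52).
- SAP 7.5.5.4 repeats the limit for the combined period: "MRI laboratory data obtained from the first day of long-term treatment up to including the last day of long-term medication".
- SAP 7.5.5.4 places "MRI laboratory data obtained from the day after the last study medication up to the last visit date of the follow-up period" in the follow-up period.
- SAP 8: "Data collected outside the analysis window (defined in Section 8.4) after subjects discontinued double-blinded study medication will be excluded from analyses".
- SAP 8.3.1, 8.5 and 12 list post-dose tolerances by assessment (1, 4, 8 or 30 days in Section 12). None of them lists MRI.

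**Rules that expect scans after stopping**

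- Protocol 5.8.6, repeated in Table 5.1-3 for the long-term period: subjects who are rescued or stop early "will be asked to return for an unscheduled MRI visit (if possible) within 4 weeks of initiating rescue medication or the Early Termination visit".
- SAP 7.5.5.4 and 8.2: for subjects rescued or stopped before Week 52/122, a value from an earlier visit stands in. Both sections add that "MRIs from week 52/122 could have been scheduled up to 4 weeks after the Rescue or Premature Treatment Discontinuation Date".
- The Week 52 row of Table 8.4 N (and Table 8.4 M) runs "Day 2 to (last day of ST double-blind treatment + 27 days"). SAP 7.5.5.4 agrees: "up to and including the last short-term double-blind dosing date + 27 days".

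**The concern.** A sub-study subject who stops drug in the long-term period is asked for a scan that will almost always fall after the last dose. The window rules leave that scan out of Week 122. The substitution rule, which names Week 122 explicitly, appears to bring it in. Nothing says which governs, so two programmers could build different Week 122 datasets from the same SAP.

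At stake is the handling of discontinuers in a sub-study of about 30 subjects per arm. The affected scans are the ones the protocol requests specifically to cover early stopping. With so few subjects, reclassifying even a few scans could shift the Week 122 estimates for visceral fat, subcutaneous fat and hepatic lipid.

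**Working it through.** **1. Reproduce the table's own days.** Target day = 7 × week + 1. Week 52: 7 × 52 + 1 = 365. Week 122: 7 × 122 + 1 = 855. Both match Table 8.4 N.

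**2. When can a long-term early-termination scan fall?** Inputs:

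- End-of-treatment visit: at most 7 days after stopping the investigational product (Protocol 3.1). I take this to be the Early Termination visit named in Protocol 5.8.6.
- Scan: at most 4 weeks = 28 days after that visit (Protocol 5.8.6).

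Days after last dose = (0 to 7) + (0 to 28) = 0 to 35. With no visit delay, it is 0 to 28.

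**3. What does each window cover?**

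| Rule | Days allowed after last dose |
|---|---|
| Week 52 row | 27 |
| Week 122 row | 0 |
| SAP 8.2 and 7.5.5.4 substitution text | up to 28, counted from discontinuation |
| Protocol request | up to 35 |

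As an illustration only, suppose every permitted combination of visit delay and scan delay is equally likely. There are 8 × 29 = 232 combinations.

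- 0 days allowed: 1/232 = 0.4% of scans kept (1/29 = 3.4% with no visit delay).
- 27 days allowed: (28 + 27 + 26 + 25 + 24 + 23 + 22 + 21)/232 = 196/232 = 84% kept (28/29 = 97% with no visit delay).
- 35 days allowed: 100% kept.

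**4. What happens to the subject's Week 122 value if the window rule is applied?** SAP 7.5.5.4 uses ANCOVA with LOCF at Week 52 but the repeated measures model at Week 122, and SAP 7.5.3 says missing observations are not imputed in that model. So either Week 122 is missing or an earlier scan is used, depending on how the substitution sentence is read.

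**5. How many subjects?** The sub-study has about 60. The documents give no discontinuation rate. Assume 10-20% over the long-term period:

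- 0.10 × 60 = 6 and 0.20 × 60 = 12. This is a ceiling under that assumption.
- Only those who stop before their Week 122 scan count. Weeks 52 to 122 are 70 of the 104 long-term weeks. If stopping is uniform in time (also assumed), 6 × 70/104 = 4.0 and 12 × 70/104 = 8.1, so about 4 to 8.
- Subtract further for subjects who never enter the long-term period and for scans not obtained, since the protocol asks for them only where possible.

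Rescued subjects remain on blinded drug (Protocol 3.5.2), so their post-rescue scans normally precede the last dose and stay in the window.

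**6. A related overlap.** The follow-up sentence in 7.5.5.4 starts the day after the last study medication with no tolerance. A short-term discontinuer's scan on day +10 is therefore both short-term (within 27 days) and follow-up. The parallel laboratory sentence in SAP 7.6.6 starts follow-up only after the tolerance has run out.

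**The case against.** The strongest case on the other side has three parts.

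**The SAP already has an MRI-specific rule that uses these scans.** SAP 8.2 and 7.5.5.4 name Week 122 and refer to scans up to 4 weeks after discontinuation. The natural candidate for the earlier-visit value is the early-termination scan. This stands to the extent that a reader may not conclude every such scan is discarded. It does not remove the problem: the rule conflicts with Table 8.4 N, with the period definitions in 7.5.5.4 itself and with SAP 8, and no precedence is stated.

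**The two time points differ for a reason.** Scheduled Week 52 scans may run to Week 54, after the short-term period has closed, so that window needs an extension even for subjects who continue. Week 122 scans (Weeks 118 to 126) fall at least 30 weeks before Week 156, so subjects still on drug need none. This is right for scheduled scans. But 2 weeks is 14 days and the Week 52 row allows 27, so scheduled scans alone do not explain it.

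**The consequence is small and its direction is not established.** A reader might infer that the Week 52 value replaces the lost scan, so that long-term discontinuers show no change after Week 52. The documents do not support that. SAP 8.2 does not say that the earlier visit is Week 52, and the Week 122 model does not carry values forward. This part of the objection stands.

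**Conclusion.** The plan gives contradictory instructions for MRI scans taken after the last long-term dose. Applied literally, the window rules exclude scans that the protocol requests and that the SAP elsewhere expects at Week 122.

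The importance is low. The Week 122 MRI endpoints are exploratory, with nominal p-values only (SAP 7.5.5), and lie outside the testing hierarchy (SAP 7.5.1). Only sub-study subjects who enter the long-term period and stop drug before their Week 122 scan are affected. Their number is unknown: below 6 to 12 at an assumed 10-20% long-term discontinuation, and about 4 to 8 if stopping is also uniform in time. A reader might take 6 to 12 as the number of scans lost, but that would require every long-term discontinuer to stop before the Week 122 scan and to return for an unscheduled one.

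The direction of any effect on the treatment comparison cannot be stated from the documents.

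**What to change.** - Extend the Week 122 row of Table 8.4 N, and the matching long-term sentence in 7.5.5.4, by one stated MRI allowance after the last dose. At least 27 days would match Week 52. Preferably use 35 days, which covers a scan 28 days after a visit that is itself 7 days after the last dose.
- State that the allowance counts from the last dose. At present the windows count from last dose, the substitution text from the discontinuation date and the protocol from the Early Termination visit.
- Start the MRI follow-up period in 7.5.5.4 only once the allowance has ended.
- Add MRI to the cutoffs in Section 12.
- State in 8.2, and in the repeated text in 7.5.5.4, that the earlier-visit value is the rescue or early-termination scan.

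The cost is a few phrases in the SAP, with no new data collection. The downside is that some Week 122 values would come from subjects a few weeks off drug, as the plan already accepts at Week 52.
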